7.7 Diet/Activity/Other Considerations

7.7.1 Diet

Patients should maintain a normal diet unless modifications are required to manage an AE such as diarrhoea, nausea or vomiting.

7.7.2 Contraception

Pembrolizumab may have adverse effects on a foetus *in utero*. Furthermore, it is not known if pembrolizumab has transient adverse effects on the composition of sperm. Non-pregnant, non-breast-feeding women may be enrolled if they are willing to use highly effective methods of contraception or are considered highly unlikely to conceive. Highly unlikely to conceive is defined as 1) surgically sterilised, or 2) postmenopausal (a woman who has not had menses for 12 months without an alternative medical cause will be considered postmenopausal), or 3) not heterosexually active for the duration of the study and the reliability of sexual abstinence needs to be evaluated in relation to the duration of the clinical trial and the preferred and usual lifestyle of the subject. Patients should start using birth control from screening throughout the study period up to 120 days after the last dose of study therapy. Male patients with partners of child bearing potential will also be required to agree to use an adequate method of contraception starting with the first dose of study therapy through 120 days after the last dose of study therapy.

The following contraception methods are considered adequate:

- Combined (estrogen and progestogen containing) hormonal contraception associated with inhibition of ovulation: oral, intravaginal or transdermal.
- Progestogen-only hormonal contraception associated with inhibition of ovulation: oral, injectable and implantable
- Intrauterine device (IUD)
- Intrauterine hormone-releasing system (IUS)
- Bilateral tubal occlusion
- Vasectomised partner- highly effective birth control method provided that partner is the sole sexual partner of the woman of childbearing potential trial participant and that the vasectomised partner has received medical assessment of the surgical success.

- Sexual abstinence- is a highly effective method only if defined as refraining from heterosexual intercourse during the entire period of risk associated with the study treatments.

Patients should be informed that taking the study medication may involve unknown risks to the foetus (unborn baby) if pregnancy were to occur during the study. In order to participate in the study they must adhere to the contraception requirement (described above) for the duration of the study and during the follow-up period. If there is any question that a patient will not reliably comply with the requirements for contraception, that patient should not be entered into the study.

7.7.3 Use in Pregnancy

If a patient inadvertently becomes pregnant while on treatment with pembrolizumab, the patient will immediately be removed from the study. The site will contact the patient at least monthly and document the patient's status until the pregnancy has been completed or terminated. The outcome of the pregnancy will be reported to the Sponsor and to MSD without delay and within 24 hours if the outcome is a serious adverse experience (e.g., death, abortion, congenital anomaly, or other disabling or life-threatening complication to the mother or newborn). The study investigator will make every effort to obtain permission to follow the outcome of the pregnancy and report the condition of the foetus or newborn to the RM-CTU without delay and within 24 hours to the Sponsor (via RM-CTU). If a male patient impregnates his female partner the study personnel at the site must be informed immediately and the pregnancy reported to the RM-CTU and followed as described above and in Section 8.

7.7.4 Use in Nursing Women

It is unknown whether pembrolizumab is excreted in human milk. Since many drugs are excreted in human milk, and because of the potential for serious adverse reactions in the nursing infant, patients who are breast-feeding are not eligible for enrolment.

7.7.5 Treatment of Overdose of IMP

For purposes of this trial, an overdose will be defined as any dose exceeding the prescribed dose for pembrolizumab by 20% over the prescribed dose. Please see section 8 for definitions and reporting procedures.

7.8 Permanent Discontinuation of Trial Medication and Withdrawal from the Study

7.8.1 Permanent Discontinuation of Trial Medication

A patient may be permanently discontinued from the trial medication for any of the following reasons:

- The subject withdraws consent.
- Confirmed radiographic disease progression, please see Section 5.3.11.4.

Note: For unconfirmed radiographic disease progression. A patient may be granted an exception to continue on treatment with confirmed radiographic progression if clinically stable or clinically improved.

- Unacceptable adverse experiences
- Intercurrent illness that prevents further administration of treatment
- The patient has a confirmed positive serum pregnancy test
- Non-compliance with trial treatment or procedure requirements
- Administrative reasons
- Completion of 35 cycles of pembrolizumab

Trial patients will not be enrolled more than once. The primary reason for discontinuation should be recorded on the CRF. Once the trial medication has been discontinued the patient should complete the end of treatment (if applicable) and safety follow-up visit procedures as listed in the schedule of study assessment (Table 3). After the end of treatment, patients will continue to be assessed for AE and SAE monitoring until completion of the safety follow up visit.

Follow-up actions for patient discontinuing the trial are as follows:

- All patients will be required to:
 - Attend a safety follow-up 30 days after their last dose of pembrolizumab,
- If a patient **progresses or begins a new anti-cancer treatment** they will be required to:
 - Undertake survival status assessments every 12 weeks until death, withdrawal of consent, lost to follow up or the end of the study.
- If a patient discontinues for reasons other than progression during treatment and **does not withdraw their consent to follow up** they will be required to:
 - Attend follow-up assessments every 9 weeks until disease progression, initiation of a new anti-cancer treatment death, end of the study. Information regarding post-study anti-cancer treatment will be collected if new treatment is initiated.

7.9 Withdrawal from the Study

Patients have the right to discontinue study treatment any time for any reason, without prejudice to their medical care. Withdrawal from the study refers to discontinuation of both study medication and study assessments; this can occur at any time according to the following reasons:

- Patient decision
- Lost to follow-up
- Death
- Principle Investigator decision

Patients may withdraw consent at any time for any reason or have trial treatment stopped at the discretion of the investigator should any untoward effect occur. In addition, a patient may be withdrawn by the Investigator or the Sponsor if enrolment into the trial is inappropriate, the trial plan is violated, or for administrative and/or other safety reasons. When a patient discontinues/withdraws prior to trial completion, all applicable activities scheduled for the final trial visit should be performed at the time of discontinuation, these are listed in the schedule of study assessments (Table 3). Any AEs which are present at that time should be followed in accordance with the safety requirements outlined in Section 8.

Patients who a) attain a complete response or b) complete 35 cycles of treatment with pembrolizumab must discontinue and may recommence for additional 17 cycles upon subsequent disease progression. Retreatment should be discussed with the Chief Investigator, the Sponsor and MSD. Pembrolizumab retreatment will be allowed only if it is in the best interest of the patients and if any other proven effective therapeutic options are no available as per standard of care and based on the investigator criteria. Study related assessment and procedures should be as for the beyond Pembrolizumab Maintenance phase (see Table 3). Patients do not need to re-sign the consent form for restarting treatment, provided their consent is on the most up-to-date version of the Patient Information Sheet Consent Form. After discontinuing treatment following assessment of complete response, these patients should return to the site for a 30 days safety follow-up visit and then proceed to the follow-up period of the study.

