5.3 Patient Replacement Strategy

Additional patients may be enrolled in a given cohort to ensure that the required number of evaluable patients in each cohort is achieved. A patient that discontinues the trial for progressive disease within 3 months of the last dose of radiotherapy will not be evaluable for DLTs and therefore will need to be replaced. A patient that discontinues the trial for a drug-related AE will not be replaced and will be counted in the evaluable population of patients for the respective cohort. However, patients found to have active pneumonitis on C1D1 of pembrolizumab or day 1 of radiotherapy will be removed from the trial and can be replaced. Also patients who

do not reach follow-up 3 months post completion of SBRT for MPM for reasons other than progression or toxicity can be replaced by new patients in that cohort to ensure there is a minimum of 3 (or 6 if required) patients in each cohort.

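### Section 7.9 lets the investigator or sponsor end a patient's study assessments without the patient asking, in conflict with Sections 7.8.1, 4.4.3, 6.1 and 6.3.11.2, which exposes PFS, OS and new non-serious toxicity data

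*Protocol*

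**What the plan says.** **Section 7.9** sets the meaning of the term: "Withdrawal from the study refers to discontinuation of both study medication and study assessments". Its list of reasons includes "Principle Investigator decision" with no condition attached. It then states that "a patient may be withdrawn by the Investigator or the Sponsor if enrolment into the trial is inappropriate, the trial plan is violated". The same sentence goes on to allow this on administrative grounds and on further safety grounds. At withdrawal, the final-visit activities are to be done and AEs present at that moment are followed under Section 8.

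**Section 7.8.1** lists reasons for permanently stopping trial medication, among them "Unacceptable adverse experiences", "Non-compliance with trial treatment or procedure requirements" and administrative reasons. The safety visit 30 days after the last pembrolizumab dose continues, and AE monitoring runs to that visit. After that, "If a patient discontinues for reasons other than progression during treatment" and the patient has not withdrawn consent to follow-up, 9-weekly assessments apply. After progression or a new anticancer therapy, survival status is sought every 12 weeks.

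**Section 5.3** keeps patients who discontinue for a drug-related AE in the evaluable population and does not replace them. For those lost early on other grounds the rule reads: "do not reach follow-up 3 months post completion of SBRT for MPM for reasons other than progression or toxicity can be replaced by new patients".

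**The concern.** Two sections attach different consequences to overlapping reasons, and nothing says which applies when a reason fits both. Under 7.8.1 the patient stays under observation. Under 7.9 observation ends, and the patient need not have asked for that.

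The trial is open label (7.2.8), so whoever takes the decision knows how the patient is doing. Removal for safety or for a violated plan can be related to outcome. Section 9.1.2 censors PFS and OS of surviving patients at the last follow-up date, which assumes that censoring carries no information about prognosis. New toxicity that is not serious would also go unobserved.

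The primary endpoint is a DLT proportion in six patients (9.1.1), so any route by which a DLT could go unrecorded needs checking as well.

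**Working it through.** **1. Do the reasons overlap?**

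| Ground | 7.8.1 (medication only) | 7.9 (medication and assessments) |
|---|---|---|
| Safety | unacceptable adverse experiences | other safety reasons |
| Non-adherence | non-compliance with treatment or procedures | trial plan violated |
| Administrative | yes | yes |
| Inappropriate enrolment | not listed | yes |
| Investigator decision, no condition | not listed | yes |

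Three grounds appear in both sections, and two appear only in 7.9.

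**2. Do other sections agree with 7.9?**
- Survival follow-up (4.4.3, 6.1) stops at death, consent withdrawal or study end. Investigator or sponsor withdrawal is not named.
- Imaging (6.3.11.2) stops at progression, new anticancer treatment, consent withdrawal, death or study end. Again it is not named.
- The 9-weekly disease follow-up in 4.4.2 and 6.1 stops at withdrawal without saying whose, whereas the trial summary in Section 1 speaks of the patient withdrawing consent.
- 7.9 itself sends complete responders who stop treatment on to follow-up, so it mixes the two concepts under one title.

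**3. Which toxicity data survive a 7.9 withdrawal?** Nominal days, with C1D1 as day 1:
- Last SBRT fraction: day 19. End of the 12-week DLT window: 19 + 84 = day 103.
- SAE reporting (8.4.1) runs 90 days from the end of study treatment. If SBRT is the last treatment, that is 19 + 90 = day 109, past the window. With a new anticancer therapy it is 30 days: 19 + 30 = day 49. Related SAEs that come to the investigator's attention later are still reportable.
- AEs present at withdrawal are followed (7.9), although 8.2 says that AEs unresolved at the last visit are followed without further CRF recording.
- New non-serious AEs have no safeguard. A grade 3 related non-haematological toxicity can be a DLT (4.2.1) without being serious.

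**4. Does 7.8.1 cover the DLT window?** Its AE monitoring ends 30 days after the last dose. With the last dose at C2 (day 22) that is day 52, which is 103 − 52 = 51 days short. At C4 (day 64) it is day 94, 9 days short. At C5 (day 85) it is day 115, which covers the window. So 7.8.1 also leaves a gap for patients who stop at C4 or earlier.

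**5. Size for PFS and OS.** The maximum sample is 6 + 12 = 18, as the protocol states. For a landmark rate, counting a lost patient first as a success and then as a failure moves the rate by 1/18 = 5.6 percentage points. Two patients give 2/18 = 11.1 and three give 3/18 = 16.7.

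**6. Size for the DLT rule, if the remaining gap is used.** The rule proceeds at 0–1 of 6 and stops at 2 or more. One DLT in six is 16.7% (exact 95% CI 0.4% to 64.1%). Two in six is 33.3% (4.3% to 77.7%).

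Let p be the true DLT rate. Let w be the share of DLT patients who are withdrawn under a non-toxicity reason before the DLT is recorded, whose DLT is never reported, and who are replaced. The observed rate is then p′ = p(1 − w)/(1 − pw), and P(proceed) = (1 − p′)⁶ + 6p′(1 − p′)⁵.

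| p | w = 0 | w = 0.10 | w = 0.25 | w = 0.50 |
|---|---|---|---|---|
| 0.25 | 0.53 | 0.58 | 0.66 | 0.79 |
| 0.33 | 0.36 | 0.41 | 0.49 | 0.66 |

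Example: for p = 0.33 and w = 0.25, p′ = 0.2475/0.9175 = 0.270 and P(proceed) = 0.49. Both p and w are assumptions, because the protocol gives neither.

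**The case against.** The strongest reply is that the protocol already protects toxicity data and that 7.9 is only a residual clause.

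- The sentence before the quoted one lets the investigator stop treatment for any untoward effect, so toxicity could be read as going there, with the withdrawal clause covering only what is left. That reading is possible, but the clause still names safety reasons, and the section's own definition ends assessments.
- A reader might infer that a patient withdrawn under 7.9 has no follow-up at all. The documents do not support this: final-visit activities, follow-up of AEs present and the SAE reporting period all remain.
- A reader might infer that withdrawing a patient with an emerging DLT readily turns 2/6 (stop) into 1/6 (proceed). This is not supported either. Such an event is an AE already present, and 5.3 neither replaces nor drops a patient who discontinues for a drug-related AE. The switch needs a toxicity to be recorded under another reason, or a non-serious DLT that arises after a withdrawal for another reason.
- A reader might take 7.8.1 as full DLT follow-up. It is not, since its AE monitoring ends at the 30-day visit.
- Section 9.1 has patients with incomplete safety observations described separately, so losses would be visible. That discloses them but does not recover the data.

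These points stand for the DLT count and narrow the concern. They do not answer the loss of progression and survival status, for which 7.9 has no safeguard beyond the final-visit activities.

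**Conclusion.** The conflict is in the text and rests on no assumption. 7.9 permits the end of assessments without the patient's request, while 7.8.1 keeps follow-up for overlapping reasons and 4.4.3, 6.1 and 6.3.11.2 do not recognise such an ending for survival follow-up or imaging.

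The main consequence is possibly informative censoring of PFS and OS, at 5.6 percentage points of best-to-worst range per patient lost before a landmark, together with loss of new non-serious toxicity. Whether the censoring would in fact be informative, and how often the clause would be used, cannot be told from the protocol.

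The effect on the primary endpoint is limited to a non-serious DLT that arises after a withdrawal recorded as violation or administrative, where 5.3 also allows replacement. The P(proceed) table applies only to that path, under assumed p and w, and is not an estimate of what will happen. The point merits an amendment but does not by itself undermine the design.

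**What to change.** 1. In 7.9, let assessments end only when the patient withdraws consent to follow-up. Record loss to follow-up as a status and death as an outcome.
2. State that an investigator or sponsor decision ends trial medication only, and that safety, disease and survival follow-up continue. This concerns observation and leaves the grounds for stopping medication as they are.
3. Reconcile 7.9 with 7.8.1, 4.4.3, 6.1 and 6.3.11.2. Where 4.4.2 and 6.1 end the 9-weekly follow-up at withdrawal, say that withdrawal of consent is meant.
4. For treated Part A patients, continue AE assessment to the end of the 12-week DLT window whatever the reason for stopping. This is a small addition, because 7.8.1 now ends AE monitoring at the 30-day safety visit.

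The cost is a wording amendment. Items 1 to 3 use visits already in the schedule, and item 4 adds a few contacts for off-treatment patients. Patients keep the right to refuse follow-up.

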8 PHARMACOVIGILANCE

8.1 Adverse events

8.1.1 Adverse Event Definition

An AE is defined as any untoward undesired or unplanned occurrence (including deterioration of a pre-existing medical condition) in a patient administered a pharmaceutical product or undertaking a protocol-specified procedure. An AE can therefore be any unfavourable and unintended sign symptom, or disease and/or laboratory or physiological observation associated with the use of a medicinal product or protocol-specified procedure but does not necessarily have to have a causal relationship to this treatment or procedure. Any worsening (i.e. any clinically significant adverse change in frequency and/or intensity) of a pre-existing condition that is temporally associated with the use of pembrolizumab, is also an AE. Changes resulting from normal growth and development that do not vary significantly in frequency or severity from expected levels are not to be considered AEs. Examples of this may include, but are not limited to, onset of menses or menopause occurring at a physiologically appropriate time. AEs may also occur in screened patients during any pre-allocation baseline period as a result of a protocol-specified intervention, including washout or discontinuation of usual therapy, diet, placebo treatment or a procedure.

8.1.2 Adverse Reaction Definition

An AE assessed by the Principal Investigator and / or Chief Investigator as reasonably likely to be related to the administration of a medicinal product or protocol-specified procedure.

8.1.3 Disease Progression

Disease progression of the cancer under study is not considered an AE unless the investigator considers it to be IMP-related or it results in hospitalisation or prolongs existing in-patient hospitalisation or death.

8.1.4 New Cancers

The development of a new cancer should be regarded as an SAE and reported accordingly.

8.1.5 Abnormal Laboratory Test Results

All clinically important abnormal laboratory test results occurring during the study will be recorded as AEs. The clinically important abnormal laboratory tests will be repeated at appropriate intervals until they return either to baseline or to a level deemed acceptable by the investigator, or until a diagnosis that explains them is made.

8.1.6 Pregnancy and Lactation

Pregnancy and lactation are not considered AEs, however these events should be reported to the RM-CTU following guidance in section 8.7

8.2 Assessing and Recording Adverse Events

All AEs will be recorded from the time of the first dose until the safety follow-up in the CRF. They will be followed up according to local practice until the event has stabilised or resolved, or the follow-up visit has taken place, whichever is the sooner. SAEs will also be recorded throughout the study. The reporting timeframe for AEs meeting any serious criteria is described in section 8.4.

Follow-up of AEs with a causality of possible, probable or highly probable will continue until the events resolve, stabilise or the patient completes the trial. Any unresolved AEs at the patient's last visit should be followed up for as long as medically indicated, but without further recording in the CRF.

If an Investigator learns of any AE that he/she consider serious, including death, at any time after a patient has completed the study and he/she considers there is a reasonable possibility that the event is related to pembrolizumab, the Investigator should notify the RM-CTU. Late toxicities will be recorded and reported as with other AEs.

The following details will be collected in the CRF for each AE:

- AE description / diagnosis
- Date of onset and date of resolution
- CTCAE grade maximum intensity
- Seriousness
- Investigator causality rating against the study medication (yes or no)
- Expectedness
- Action taken with regard to study medication
- Outcome

For the pre-registration period AEs will not be collected in patients that have not undergone any protocol-specified procedure or intervention. If the patient requires a blood draw, fresh tumour biopsy etc. for the study then the patient will be required to consent to the main study and AEs will be captured as described above.

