3.2.2 Secondary Endpoints

- To assess acute toxicity rates (defined as up to 12 weeks after last SBRT fraction) using CTC AE v5.0.
- To assess late toxicity rates (defined as from 12 weeks after last SBRT fraction in MPM until 28 days after the last dose of pembrolizumab) using CTCAE version 5.0.
- To calculate the ORR, DCR and DOR using mRECIST and RESIST 1.1.
- To calculate the ORR and DCR in epithelioid versus sarcomatoid histological subtype using mRECIST and RESIST 1.1.
- To assess the frequency of PD-1/PD-L1 expression distribution in responders and non-responders.
- To measure the PFS and OS at 6 and 12 months.

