In the initial safety cohort, a minimum of 3 patients will be treated at the SBRT dose of 30Gy in 3 fractions combined with pembrolizumab. The gap left between the treatments of each subsequent patient will start after the second cycle of Pembrolizumab in the previous dosed patient to mitigate against multiple patients suffering from acute toxicity. The DLT period for this study is 12 weeks from the last dose of SBRT (i.e. at C6D1). Patients included in Part A will be considered by the Safety Review Committee (SRC) once the 3rd and 6th patient in the Part A cohort has completed the DLT period. If 0 out of 3 patients experience a DLT, or if 1 out of 3 patients experience a DLT in Part A, then the cohort will be expanded to 6 patients. If 1 in 6 patients experience a DLT, then it will be acceptable to move forward to the expansion cohort (Part B). However, if ≥ 2 in 6 patients (or more than 1 in the first 3 patients) experience a DLT then the maximum administered dose

(MAD) will have been reached. If the MAD is seen at a dose level of 30 Gy in 3# then the study will be terminated.

While waiting for 3 or 6 patients to complete the DLT period, no additional patients will be recruited. Further patients can only be recruited after the SRC has reviewed the toxicity data for the cohort to proceed to Part B. Patients obtaining complete response or having completed 35 cycles of pembrolizumab must discontinue and may recommence for additional 17 cycles upon subsequent disease, the CI/PI will need to discuss with the sponsor and MSD, on a case by case basis for the continuation of pembrolizumab.

Table 1: SBRT dose level and pembrolizumab dosing during the initial safety cohort and expansion phase.

Dose Level	Pembrolizumab Dose	SBRT to part of a MPM lesion
Initial safety cohort	200 mg i.v. over 30 minutes, every 3 weeks	30 Gy in 3# (Monday, Wednesday, Friday)
Expansion cohort	200 mg i.v. over 30 minutes, every 3 weeks	30 Gy in 3# (Monday, Wednesday, Friday)

SBRT: Stereotactic Ablative Body Radiotherapy; Gy: Gray; i.v.: intravenous; mg: milligrams; #: fraction.

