4.2.1 Dose Limiting Toxicities

Acute toxicity will be assessed up to and including 3 months following the final fraction of radiotherapy (i.e. at C6D1). The MRC dyspnoea score (Appendix 2) will be used to assess dyspnoea at baseline/on treatment and the Common Toxicity Criteria for Adverse Events (CTCAE) version 5.0 will be used to grade all drug and SBRT observed toxicities (Appendix 4). The SRC will consider expansion after the 6th patient in the initial safety cohort has completed the DLT period and reviewed the toxicities before recruitment to the expansion cohort Part B.

Any DLT must be a toxicity that is considered probably, possibly or definitely related to the combination of pembrolizumab and SBRT. DLT is defined as follows:

Haematologic:

- Neutropenia with fever grade 3 or neutropenia grade 4
- Thrombocytopenia with bleeding grade 3 or thrombocytopenia grade 4

Non-Haematologic:

Any ≥ 3 non-haematological toxicity which is definitely, probably or possibly related to the combination of pembrolizumab and SBRT for pleural mesothelioma including the following:

- Increased MRC dyspnoea score > 2 grades from baseline and/or acute dyspnoea grade ≥ 4 (or CTCAE dyspnoea grade ≥ 3) persisting for > 7 days (including weekend).
- Pneumonitis grade ≥ 3 persisting for > 7 days (including weekend).
- Oesophagitis grade ≥ 3 persisting for > 7 days (including weekend).
- Toxicity leading to interruption of radiotherapy for > 7 days (including weekend).

Progression of the study will not proceed until the following criteria are satisfied by the SRC:

- If 0 out of 3 patients experience a DLT, or if 1 out of 3 patients experience a DLT, a further 3 patients will be recruited at the dose level in the initial safety cohort.
 - If 0 out of 6 patients experience a DLT, or if 1 out of 6 patients experience a DLT, then progression to Part B of the study can proceed.
 - If ≥ 2 out of 6 patients (or more than 1 in the first 3 patients) experience a DLT, then there will be no Part B expansion phase and the study will be terminated.

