4.4 Follow-Up after stopping Pembrolizumab

4.4.1 30 Day Safety Follow-Up Visit

All patients will be required to attend a safety follow-up visit 30 days after the last dose of pembrolizumab or before the initiation of a new anti-cancer treatment, whichever comes first. Patients who restart treatment on disease progression, once completed the treatment period will also attend to a safety follow-up visit as detailed above. All adverse events (AEs) and serious adverse events (SAEs) that occur prior to the safety follow-up visit should be reported as described in section 8. After the safety follow-up any unresolved AEs at the patient's last visit should be followed up for as long as medically indicated, but without further recording in the CRF.

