6.3.2 Adverse Event (AE) Monitoring

The Investigator or qualified designee will assess each patient for potential new or worsening AEs as specified in the schedule of study assessments (Table 3) and more frequently if clinically indicated. AEs will be graded and recorded from confirmation of entry into the trial until the patients 30 day safety follow up visit according to CTCAE v5.0 (see Appendix 4). Toxicities will be characterised in terms regarding seriousness, causality, toxicity grading, and action taken with regard to trial treatment.

All AEs of unknown aetiology associated with pembrolizumab exposure should be evaluated to determine if it is possibly an event of clinical interest (ECI) or a potentially an immune related adverse event (irAE). See Appendix 5 regarding the identification, evaluation and management of AEs of a potential immunological aetiology. Please refer to section 8 for detailed information regarding the assessment and recording of AEs.

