7.1.2 Toxicity Assessments

Dyspnoea score and toxicity grading with CTCAE v5.0 will be recorded and will include pneumonitis, lung fibrosis, oesophagitis, skin toxicity, myelitis and fatigue. All other AEs will be documented in addition.

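### CRF recording of new non-serious AEs stops about 30 days after the last pembrolizumab dose, before the 12-week post-SBRT DLT and acute-toxicity windows close in patients who stop by cycle 4

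*Protocol*

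**What the plan says.** Several sections of the Protocol end AE recording or monitoring at the safety visit.

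- Section 8.2: "All AEs will be recorded from the time of the first dose until the safety follow-up in the CRF".
- Section 6.3.2: "AEs will be graded and recorded from confirmation of entry into the trial until the patients 30 day safety follow up visit".
- Section 7.8.1: "After the end of treatment, patients will continue to be assessed for AE and SAE monitoring until completion of the safety follow up visit".
- Section 4.4.1 dates the visit: "safety follow-up visit 30 days after the last dose of pembrolizumab or before the initiation of a new anti-cancer treatment, whichever comes first". It adds that AEs still open at that point are followed clinically but no longer entered in the CRF.

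The toxicity windows are counted from radiotherapy instead.

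- Section 4.2: "The DLT period for this study is 12 weeks from the last dose of SBRT (i.e. at C6D1".
- Section 3.2.2 gives the acute-toxicity endpoint the same length: "defined as up to 12 weeks after last SBRT fraction".
- Section 4.2.1: "Acute toxicity will be assessed up to and including 3 months following the final fraction of radiotherapy (i.e. at C6D1".
- Section 7.1.2, with no end date: "Dyspnoea score and toxicity grading with CTCAE v5.0 will be recorded and will include pneumonitis, lung fibrosis, oesophagitis, skin toxicity, myelitis and fatigue".

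The late-toxicity endpoint in section 3.2.2 opens at the 12-week point and closes 28 days after the last pembrolizumab dose.

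**The concern.** The end of data collection depends on the last pembrolizumab dose, while the endpoints depend on the last SBRT fraction. For a patient who stops pembrolizumab early, collection ends first. A site that follows section 8.2 literally would not enter a non-serious toxicity that starts after the safety visit but inside the protocol's own DLT and acute windows. A site that follows sections 4.2.1 and 7.1.2 would.

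Worsening events are exposed too. Section 8.3.1 treats a change of grade as a new AE record, yet section 4.4.1 stops CRF entry for unresolved events at the safety visit.

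Safety is the primary question of this trial, and Part A turns on one versus two DLTs in six patients, so completeness of toxicity data inside the stated window matters. This is not something an analysis plan could repair: events that were never collected cannot be recovered later.

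**Working it through.** **Inputs.** SBRT is given on C1D15, C1D17 and C1D19, and pembrolizumab every 21 days (section 4.2). The safety visit is 30 days after the last dose (section 4.4.1), with a window read from Table 3 as ±7 days. Follow-up for patients who stop without progression is every 9 weeks (section 4.4.2), counted from the safety visit in Table 3. Doses are assumed to be on schedule.

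**The plan's own figure.** The window ends on day 19 + 84 = 103. C6D1 is day 1 + 21 × 5 = 106. The two agree within the ±3-day dosing window, so the protocol's equation of 12 weeks with C6D1 is reproduced.

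**Formulas.** For a last dose at cycle k:
- dose day = 1 + 21(k − 1)
- safety visit = dose day + 30
- uncovered days = 103 − safety visit (or 106 − safety visit), not below 0
- next follow-up visit = safety visit + 63
- late window = dose day + 28 − 103, not below 0

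| Last dose | Dose day | Safety visit | Uncovered to day 103 (visit ±7) | Share of 84 days | Uncovered to day 106 | Next 9-weekly visit | Late window (days) |
|---|---|---|---|---|---|---|---|
| C1 | 1 | 31 | 72 (65–79) | 86% | 75 | 94 | 0 |
| C2 | 22 | 52 | 51 (44–58) | 61% | 54 | 115 | 0 |
| C3 | 43 | 73 | 30 (23–37) | 36% | 33 | 136 | 0 |
| C4 | 64 | 94 | 9 (2–16) | 11% | 12 | 157 | 0 |
| C5 | 85 | 115 | 0 | 0% | 0 | 178 | 10 |
| C6 | 106 | 136 | 0 | 0% | 0 | 199 | 31 |

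**Threshold.** There is no gap once the last dose is on or after day 103 − 30 = 73 (day 76 if the window closes at C6D1). C4 is therefore the last cycle with a gap. The ±7-day visit window alone does not close it, since 94 + 7 = 101. An earlier safety visit because of new treatment would lengthen any gap.

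**Follow-up visits.** For C2, C3 and C4 the next visit falls nominally 12, 33 and 54 days after day 103. For C2 the range is day 101 to 129 when both ±7-day windows are used. Section 4.4.2 describes these visits as monitoring disease status.

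**Who is exposed for the primary endpoint.** Section 5.3 replaces patients who leave for progression within 3 months of radiotherapy, but keeps as evaluable those who leave for a drug-related AE. The exposed patient is therefore one who stops for a drug-related AE that is not itself a DLT. Table 9 gives one route: a grade 2 infusion reaction despite premedication leads to permanent discontinuation. If this happens at C2, the last dose is day 22 and the safety visit is day 52. Tables 8 and 10 give another, since recurrent grade 2 pneumonitis leads to discontinuation but is below the grade 3 DLT threshold in section 4.2.1.

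**The case against.** The strongest case on the other side has four parts.

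1. *Table 3 may schedule AE assessment at the 9-weekly visits.* Section 6.3.2 refers to that table, and the CRF captures onset dates, so a visit on day 115 could still pick up an event that began inside the window. However, the column positions of the AE row could not be read reliably, and different rows point to different placements. If the row does extend to those visits, it contradicts sections 4.4.1, 6.3.2, 7.8.1 and 8.2 and does not settle the matter.

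2. *Most DLT-grade events are serious.* Many grade 3 and 4 events would involve hospitalisation or a threat to life. SAEs are recorded throughout the study under section 8.2, and related SAEs are reportable at any time under section 8.4.1. This stands and is why the effect on the DLT count is small. It does not reach non-serious events, which are part of the acute-toxicity rate.

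3. *DLT completeness has its own rules.* The Safety Review Committee (SRC) meets only after patients complete the DLT period, section 4.2.1 requires assessment to 3 months, and section 5.3 ties evaluability to the 3-month follow-up. Nothing says that the SRC sees only the AE page. This also stands as a limit, but these rules sharpen the conflict with section 8.2 because they presuppose observation that section 8.2 stops. Section 9.1 describes incompletely observed patients separately, but that does not supply their events.

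4. *The late window is simply empty for early stoppers, by definition.* That is correct for a descriptive endpoint, but the rate then needs a stated denominator.

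**Conclusion.** The concern holds. For an on-schedule last dose at C2, C3 or C4, recording of new non-serious AEs stops 51, 30 or 9 days before the 84-day window closes, or 72 days if only C1 is given. From C5 there is no gap on the nominal schedule.

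The acute-toxicity rate can be under-ascertained in any patient whose last dose is C4 or earlier. The DLT count is exposed only in the few evaluable patients who stop for a drug-related AE that is not a DLT and then have a later non-serious DLT. The late-toxicity rate describes late SBRT toxicity only in patients who stay on pembrolizumab to at least C5.

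The Protocol gives no rate of stopping by C4, so neither the number of affected patients nor any change in the Part A decision can be stated. The figures assume on-schedule dosing and SBRT completed on day 19. The point should be fixed; it does not invalidate the design.

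A side point, on which the conclusion does not depend, is that the causality wording is not aligned. Section 8.2 collects a yes/no rating against study medication and also mentions a highly probable level that the 8.3.2 scale lacks. Section 8.3.2 opens with treatment or procedure but defines its scale against the IMP. Section 4.2.1 attributes a DLT to the combination with SBRT.

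**What to change.** - **Sections 4.4.1, 6.3.2, 7.8.1 and 8.2:** for every patient who received SBRT, record AEs in the CRF until the later of the safety visit and 12 weeks after the last SBRT fraction. Recording would then end on day 103 for a last dose at C1 to C4 and stay at day 115 for C5 and day 136 for C6. Check that the Table 3 AE row agrees.
- **Early stoppers:** make a telephone contact at about day 103, or ask at the next follow-up contact for events with onset inside the window. Record the start date of any new anti-cancer therapy so that later events can be shown separately.
- **Section 3.2.2:** state that the late-toxicity rate applies only to patients with a non-empty window, or define the end of that window by SBRT follow-up.
- **Sections 8.2 and 8.3.2:** reconcile the causality wording with section 4.2.1, for example with a CRF causality item for SBRT beside the one for pembrolizumab.

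The cost is wording in a few sections, one CRF item and one extra contact for patients who stop by C4. Reported toxicity rates may be slightly higher, and some added events may be confounded by new therapy. No DLT criterion or clinical rule changes.
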